## 1.2. Study Objectives

### 1.2.1. Primary Objective

The primary objective of Part B of the study is to demonstrate the efficacy of multiple doses of dupilumab over 16 weeks of treatment when administered concomitantly with TCS in pediatric patients, 6 months to less than 6 years of age, with moderate-to-severe AD.

### 1.2.2. Secondary Objectives

The secondary objective of Part B of the study is to assess the safety and immunogenicity of multiple doses of dupilumab over 16 weeks of treatment when administered concomitantly with TCS in patients 6 months to less than 6 years of age with moderate to severe AD.

### 1.2.3. Modifications from the Statistical Section in the Final Protocol

The following modifications have been implemented in this SAP.

Item	Change from the Protocol	Reasons
Per protocol set (PPS) population	There will be no analysis using PPS population.	Not required by ICH.
Imputation for binary responses	Missing data due any reasons other than rescue treatment, AE, lack of efficacy (LOE) or withdrawn consent from study will be imputed by multiple imputation (MI).	Consistent with imputation method for continuous endpoints.
Imputation for continuous responses	Patients with missing values at week 16 due to rescue treatment, withdrawn consent, AE, and lack of efficacy will be imputed by postbaseline worst-observation-carried-forward (WOCF) if there is at least one non-missing postbaseline value or by baseline value if there is no postbaseline value.	Clarify WOCF and add that missing due to withdrawn consent should be imputed by WOCF.
Onset of action analysis in percent change from baseline weekly average of daily worst scratch/itch NRS score, proportion of $NRS \geq 3$ ,	Add the following analysis: Onset of action in percent change from baseline weekly average of daily worst scratch/itch NRS score can be assessed by providing a nominal p-value at each assessment visits. The analysis will be carried out on the FAS population only. Using this analysis, the first assessment visit at which $p < 0.05$ for the difference from placebo in the weekly average of daily worst scratch/itch NRS score that remains $p < 0.05$ at subsequent weekly measurements through week 16	To assess the onset of effect on these endpoints.

NRS<math>\geq</math>4,                  IGA 0/1, and                  EASI-75
	
can be identified. The similar analysis will be carried out on the following binary responses:
 
 
• IGA 0/1
 
• EASI-75
 
• Improvement (reduction) of weekly average of daily worst itch NRS score <math>\geq</math>3 from baseline
 
• Improvement (reduction) of weekly average of daily worst itch NRS score <math>\geq</math>3 from baseline
 
	

Additional endpoint for TCS use
	
 
• Mean weekly dose of medium and/or high potency TCS through week 16
 
	
This endpoint measures the steroid sparing effect of study drug on medium or high potency TCS, which is considered to be clinically relevant.

**1.2.4. Revision History for SAP Amendments**

[figure not shown]
None.

## 2. INVESTIGATIONAL PLAN

### 2.1. Study Design and Randomization

The study, R668-AD-1539 is being conducted in two parts.

**Figure 1: Overall Design**

The Part A of AD-1539 has been completed. The CSR has been finalized and approved in Dec 2020. This document focuses on Part B of the study only.

AD-1539 B is a randomized, double-blind, placebo-controlled, parallel-group study to investigate the efficacy and safety of SC dupilumab when administered concomitantly with TCS in pediatric patients,  $\geq 6$  months to  $< 6$  years of age, with moderate-to-severe AD. Approximately 160 patients are planned to be randomized in the study. The number of patients with moderate AD (IGA=3) is capped at approximately 40 patients. Figure 1 shows the overall design of AD-1539 (Parts A and B).

[figure not shown]
Part B consists of the following 3 periods: a screening period of up to 56 days (including 2 weeks of TCS standardization), a treatment period of 16 weeks, and a follow-up period of 12 weeks (Figure 3). Patients who enrolled in Part A of the study are not eligible to participate in Part B.

Patients who continue to meet eligibility criteria at baseline undergo day 1/baseline assessments. Patients are randomized in a 1:1 ratio stratified by baseline body weight ( $\geq 5$ - $< 15$  kg and  $\geq 15$ - $< 30$  kg), baseline disease severity (IGA=3 and 4), and region/country (North America and Europe). Approximately 160 patients are randomized to 1 of the following 2 treatment regimens (Figure 2):

- dupilumab Q4W tiered fixed-dose (200 mg or 300 mg) treatment regimen:
  - Patients with baseline weight  $\geq 5$  to  $< 15$  kg receive an SC injection of 200 mg dupilumab (1.14 mL of a 175 mg/mL solution) on day 1 and then 200 mg Q4W from week 4 to week 12.
  - Patients with baseline weight  $\geq 15$  to  $< 30$  kg receive an SC injection of 300 mg dupilumab (2 mL of a 150 mg/mL solution) on day 1 and then 300 mg Q4W from week 4 to week 12.
- placebo Q4W treatment regimen: patients receive matching placebo on day 1 and then Q4W from week 4 to week 12.
  - In the  $\geq 5$  to  $< 15$  kg weight stratum, patients randomized to placebo receive Q4W injections of placebo (1.14 mL) matching 200 mg dupilumab.

- In the  $\geq 15$  to  $< 30$  kg weight stratum, patients randomized to the placebo group receive Q4W SC injections of placebo (2 mL) matching 300 mg dupilumab.

**Figure 2 Randomization Scheme for Part B**

Note: Randomization will be stratified by baseline weight ( $\geq 5$ - $< 15$  kg and  $\geq 15$  to  $< 30$  kg), baseline disease severity (IGA=3, 4), and region/country (North America and Europe^).

## 2.2. Statistical Hypothesis

For the comparison of the dupilumab treatment group to placebo, the following hypotheses of the primary endpoint will be tested, where  $p_d$  is the true proportion of patients achieving IGA 0 or 1 at week 16.

Proportion of patients achieving IGA 0 or 1 at week 16

- Null hypothesis ( $H_0$ ):  $p_p = p_d$ , i.e., the proportion of patients achieving IGA 0 or 1 at week 16 is the same between the dupilumab group and the placebo group.
- Alternative hypothesis ( $H_1$ ):  $p_p \neq p_d$ , i.e., the proportion of patients achieving IGA 0 or 1 at week 16 is different between the dupilumab group and the placebo group.

The following co-primary endpoints (**only in the European Union [EU] and EU Reference Market Countries**) will be tested:

Proportion of patients achieving IGA 0 or 1 at week 16

- Null hypothesis ( $H_0$ ):  $p_p = p_d$ , i.e., the proportion of patients achieving IGA 0 or 1 at week 16 is the same between the dupilumab group and the placebo group.

- Alternative hypothesis ( $H_1$ ):  $p_p \neq p_d$ , i.e., the proportion of patients achieving IGA 0 or 1 at week 16 is different between the dupilumab group and the placebo group.

Proportion of patients with EASI-75 ( $\geq 75\%$  improvement from baseline) at week 16

- Null hypothesis ( $H_0$ ):  $p'_p = p'_d$ , i.e., the proportion of patients with EASI-75 at week 16 is the same between the dupilumab group and the placebo group.
- Alternative hypothesis ( $H_1$ ):  $p'_p \neq p'_d$ , i.e., the proportion of patients with EASI-75 at week 16 is different between the dupilumab group and the placebo group.

### 2.4. Study Plan (Part B)

The study consists of the following periods (Figure 3):

1. Screening of up to 56 days, including TCS standardization period of 2 weeks
2. Treatment period of 16 weeks, and
3. Follow-up of 12 weeks (for patients who do not enter the OLE study, R668-AD-1434)

**Figure 3: Study Flow Diagram**

TCS Std: topical corticosteroid standardization

Note: The length of the screening period is not fixed but must not exceed 56 days (including TCS standardization). The length of the TCS standardization period is fixed at 14 days. Moisturizers are to be applied at least twice daily during the 7 consecutive days prior to randomization (not including day of randomization) and are to be used throughout the study. At least 11 of the 14 total applications of moisturizers prior to randomization must be applied for the patient to remain eligible for the study.

Starting on day -14, all patients will be required to initiate treatment with low potency TCS using a standardized regimen (see Section 5.2 for details).

During the treatment period, patients will have in-clinic visits at baseline, week 1, week 2, and week 4, then monthly in-clinic visits through week 16 with weekly telephone visits in between the clinic visits.

Safety and laboratory assessments, samples for dupilumab concentration and ADA response to dupilumab, and efficacy assessments will be performed or collected at specified time points throughout Part B of the study according to the schedule described in study protocol. The end of treatment period visit will occur at week 16, 4 weeks after the last dose of study drug. The primary endpoint (and co-primary endpoint for EU and EU Reference Market Countries only, proportion of patients with an EASI-75, which is a key secondary endpoint for US) will be assessed at this visit.

An OLE study (R668-AD-1434) in patients aged 6 months to <18 years old is currently ongoing. Patients who complete the treatment period in Part B may subsequently be eligible to participate in the OLE study (refer to R668-AD-1434 Protocol).

Patients who decline to participate in the OLE will enter a follow-up period of 12 weeks. Follow up visits will occur every 4 weeks from week 20 through week 28. During the follow-up period, patients will be monitored for safety and tolerability and have laboratory and clinical assessments

### 3. ANALYSIS POPULATIONS

In accordance with guidance from the International Conference of Harmonization of Technical Requirements for Registration of Pharmaceuticals for Human Use (ICH) guideline ICH E9 Statistical Principles for Clinical Trials (1998), the following populations of analysis will be used for all statistical analyses.

#### 3.1. The Full Analysis Set (FAS)

The full analysis set (FAS) includes all randomized patients. Efficacy analyses will be based on the treatment allocated at randomization (as randomized). All efficacy variables will be evaluated in the FAS, which will be the primary analysis set.

#### 3.2. The Safety Analysis Set (SAF)

The safety analysis set (SAF) includes all randomized patients who receive at least one dose of study drug and will be analyzed as treated. Treatment compliance/administration and all clinical safety variables will be summarized based on the SAF.

The “as treated” assignments will be made as follows:

**Table 1: Assignment of “as-treated” arms**

Randomized to	Treatment Received	Treatment Assignment
Dupilumab	All placebo	Placebo
Dupilumab	≥ 1 Dupilumab dose	Dupilumab
Placebo	>=1 Dupilumab dose	Dupilumab

In addition:

- Nonrandomized but treated patients will not be part of the safety population (SAF); however, their safety data will be presented separately.
- Randomized patients for whom it is unclear whether they took the study drug will be included in the safety population as randomized.

For safety summaries, three analysis periods are defined as follows:

- 16-week treatment period is defined as
  - Day 1 to the study completion date of the planned Week 16 visit (or study day 113 starting from the first dose of study drug if the date of the Week 16 treatment visit is unavailable) for those patients who completed the 16-week treatment period
  - Day 1 to the date of early termination visit, for those patients who did not complete the 16-week treatment period

- Follow-up period is defined as the date after the week 16 visit date (or study day 113 starting from the first dose of study drug if the date of Week 16 treatment visit is unavailable) to the date of the end of study visit
- Overall study Period is defined as Day 1 to the date of the end of study (EOS) visit

The SAF will be the basis for the analyses for the treatment period and overall study period; however, for the analyses for the follow-up period, only a subset of the SAF will be included, which is defined as the patients who entered the follow-up period and had at least one visit after the week 16 treatment visit (EOT).

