7.2.2. Serious Adverse Events

All SAEs, regardless of assessment of causal relationship to study drug must be reported to the sponsor (or designee) within 24 hours. Refer to the investigator site binder for the procedure to be followed.

Information not available at the time of the initial report must be documented in a follow-up report. Substantiating data such as relevant hospital or medical records and diagnostic test reports may also be requested.

The investigator must promptly report to the Institutional Review Board/Ethics Committee (IRB/EC) all unanticipated problems involving risks to patients. This includes death from any cause and all SAEs related to the use of the study drug. It is recommended that all SAEs be reported to the IRB/EC, regardless of assessed causality.

In the event the investigator is informed of an SAE after the patient completes the study, the following will apply:

- SAE with an onset within 30 days of the end of study/early termination visit - the SAE will be reported to the sponsor. The investigator should make every effort to obtain follow-up information on the outcome until the event is considered chronic and/or stable.
- SAE with an onset day greater than 30 days from the end of study/early termination visit - only fatal SAEs and those deemed by the investigator to be drug-related SAEs will be reported to the sponsor. The investigator should make every effort to obtain follow-up information on the outcome of a drug-related SAE until the event is considered chronic and/or stable.

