9.5.3.1. Adverse Events

Definitions

For safety variables, 2 observation periods are defined separately for parts A and B:

- The pre-treatment period is defined as the time from signing the ICF to before the first dose of study drug.
- The treatment-emergent period is defined as the day from the first dose of study drug to the end of the study. In Part B, the treatment-emergent period includes the 16-week treatment period and follow-up period.
 - Treatment period: date of the first dose of study drug to week 16 visit date (study day 113 starting from the first dose of study drug if week 16 visit date is unavailable) or early termination date, whichever comes first.
 - Follow-up period: date after week 16 visit date (study day 113 starting from first dose of study drug if week 16 visit date is unavailable) or early termination date, to end of study. Patients who continue into the OLE after the treatment period will not have a follow-up period.

Treatment-emergent AEs are defined as those that are not present at baseline or represent the exacerbation of a pre-existing condition during the overall study period.

Analysis

All AEs reported in this study will be coded using the currently available version of the Medical Dictionary for Regulatory Activities (MedDRA®). Coding will be to lowest level terms. The verbatim text, the preferred term (PT), and the primary system organ class (SOC) will be listed.

Summaries of all TEAEs by treatment group will be provided separately for parts A and B. The summary will include:

- The number (n) and percentage (%) of patients with at least 1 TEAE by SOC and PT
- TEAEs by severity (according to the grading scale outlined in Section 7.3.1), presented by SOC and PT
- TEAEs by relationship to treatment (related, not related), presented by SOC and PT

Deaths and other SAEs will be listed and summarized by treatment group.

Treatment-emergent adverse events leading to permanent treatment discontinuation will be listed and summarized by treatment group.

In addition, to account for potential differential exposure time, the exposure-adjusted analyses for part B may be provided. The details will be specified in the SAP.

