**Secondary endpoints for safety:**

- Incidence of skin infection TEAEs (excluding herpetic infections) through week 16\*
- Incidence of SAEs through week 16

\*Adjudicated by study medical director.

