## **4.5. Safety Variables**

### **4.5.1. Adverse Events and Serious Adverse Events Variables**

Adverse events and serious adverse events (SAE) will be collected starting from the time of informed consent signature and at each visit until the end of the study. All adverse events are to be coded to a "Preferred Term (PT)", "High Level Term (HLT)" and associated primary "System Organ Class (SOC)" according to the Medical Dictionary for Regulatory Activities (MedDRA).

The criteria for determining whether an abnormal laboratory, vital sign or ECG finding should be reported as an AE are as follows:

- Test result is associated with accompanying symptoms, and/or
- Test result requires additional diagnostic testing or medical/surgical intervention, and/or
- Test result leads to a change in dosing (outside of protocol-stipulated dose adjustments) or discontinuation from the study, significant additional concomitant drug treatment, or other therapy

The pre-treatment period is defined as the period from the patient providing informed consent up to the first dose of study drug. The treatment and follow-up period is defined as the period from the administration of first study dose to the EOS visit.

Pre-treatment AEs and treatment emergent AEs (TEAEs) are defined as follows:

- Pre-treatment AEs are AEs that developed or worsened in severity during the pre-treatment period.

- Treatment-emergent AEs (TEAEs) are AEs that developed or worsened in severity compared to the baseline during the treatment and follow-up period. As only worsening pre-existing AEs and new AEs reported during the treatment and follow-up period will be collected in the study, all AEs collected during the treatment and follow-up period are considered TEAEs.
- TEAEs during the 16 week treatment period are AEs with onset after the first dose up to the week 16 visit date (study day 113 if the week 16 visit date is missing) or early termination visit, whichever is earlier. TEAEs that have an onset during the 16 week treatment period and continued afterwards into the follow-up period will be counted only once as TEAEs during the 16 week treatment period.
- TEAEs during the follow-up period are AEs with onset after the week 16 visit date up to the end of the study.

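### For a child withdrawn before week 16, an SAE reported after the early termination visit can fall between the SAP's treatment and follow-up periods and be missed by the incidence tables

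*SAP*

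**What the plan says.** SAP section 3.2 defines three safety periods.

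- **Treatment period**, for a child who does not complete 16 weeks: "Day 1 to the date of early termination visit, for those patients who did not complete the 16-week treatment period".
- **Follow-up period**: "Follow-up period is defined as the date after the week 16 visit date", with Day 113 as the fallback when there is no week 16 date. The follow-up analyses use only part of the safety set: "the patients who entered the follow-up period and had at least one visit after the week 16 treatment visit (EOT".
- **Overall period**: "Overall study Period is defined as Day 1 to the date of the end of study (EOS) visit".

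SAP section 4.5.1 repeats the ET cut-off for treatment-period events and adds: "TEAEs during the follow-up period are AEs with onset after the week 16 visit date up to the end of the study".

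Protocol section 9.5.3.1 also stops the treatment period at early termination when that comes first. Its follow-up period, however, begins after the week 16 date "or early termination date, to end of study. Patients who continue into the OLE after the treatment period will not have a follow-up period". The table of modifications in SAP section 1.2.3 does not mention that this second starting point was dropped.

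Protocol section 7.2.2 covers events that the investigator hears of later: "SAE with an onset within 30 days of the end of study/early termination visit - the SAE will be reported to the sponsor". After 30 days only fatal or drug-related SAEs are reportable.

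"Incidence of SAEs through week 16" is a named secondary safety endpoint in SAP section 4.4.2 and Protocol section 8.2.2.

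**The concern.** The protocol's periods join up: one ends at ET and the next begins after it. The SAP keeps the first boundary and moves the second to week 16 or Day 113. This leaves an interval for early leavers in which SAEs can still be reported but neither period counts them.

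Under SAP section 5.7.1, the denominator is the number of patients in the arm for the period concerned, and the whole safety set is the basis for the treatment period. The child therefore stays in the denominator while the event is left out of the numerator. What is at stake is the completeness of a secondary safety endpoint in children under 6 years, for whom SAE counts are likely to be small.

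**Working it through.** **Week 16 day.** 16 × 7 + 1 = 113, which agrees with the SAP's Day 113.

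**The periods side by side, for a child withdrawn at ET with no week 16 or EOS visit.**

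| Period | SAP | Protocol 9.5.3.1 |
|---|---|---|
| Treatment | Day 1 to ET | first dose to ET |
| Follow-up | after Day 113, and only patients with a visit after week 16 | after ET, to end of study |
| Overall | Day 1 to EOS visit; no date given for this child | first dose to end of study |

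**Worked record.** ET on Day 64, SAE onset on Day 75.
- Reportable: 75 − 64 = 11 days, within 30.
- SAP treatment period: no, because 75 > 64.
- SAP follow-up period: no, because 75 ≤ 113, and the child has no visit after week 16.
- SAP overall period: undetermined. The schedule of events lists ET separately from EOS (visit 22, week 28), and the SAP sets no end date for a child without an EOS visit.
- Protocol follow-up period: yes, because 75 > 64.

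**Width of the gap.** Reportable days that fall after ET and no later than Day 113 = min(30, 113 − ET day).
- ET on Days 1 to 83: 30 days (at Day 83, 113 − 83 = 30)
- ET on Day 85: 28 days
- ET on Day 99: 14 days
- ET on Day 112: 1 day

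**Size of one omission.** The plan has 80 patients per arm (SAP section 2.3), so one child is 1/80 = 1.25 percentage points. For scale, Protocol section 1.2.2 gives adult phase 3 SAE rates of 1% to 3% on dupilumab and 5% to 6% on placebo. Applying them to this age group is an assumption:
- dupilumab: 80 × 1% to 3% = 0.8 to 2.4 children with an SAE
- placebo: 80 × 5% to 6% = 4.0 to 4.8 children

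**Expected number missed.** No ET rate is given for part B, so assume 5% to 20% of an arm (4 to 16 children), a constant SAE rate over 112 days, and a full 30-day gap.
- dupilumab, risk per child: 1% × 30/112 = 0.27%, to 3% × 30/112 = 0.80%
- dupilumab, per arm: 4 × 0.27% = 0.01, to 16 × 0.80% = 0.13
- placebo, risk per child: 5% × 30/112 = 1.34%, to 6% × 30/112 = 1.61%
- placebo, per arm: 4 × 1.34% = 0.05, to 16 × 1.61% = 0.26

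Early leavers may be at higher risk than this. The documents give no basis for estimating by how much.

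**The case against.** Several points on the other side stand.

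- **The protocol also ends the treatment period at ET.** A reader might infer that the SAP's omission alone removes the event from the week 16 endpoint. It does not. Restoring the protocol wording would place the Day 75 event in follow-up and leave a treatment-period count unchanged. Nor does the SAP say outright that the endpoint means the 16-week treatment period, although that is the only defined period that matches.
- **Absence from every SAP period is not established.** It is tempting to say that the event is in no period at all. Exclusion from treatment and follow-up is explicit, but exclusion from the overall period is inferred from the missing EOS visit. Protocol section 3.1.3 defines the end of study as the last patient's last visit. If that date were used, the overall table would include the event. The SAP ties the period to the EOS visit and leaves this open.
- **Reporting after ET is passive.** It depends on the investigator being told, and the documents do not say how such reports reach the analysis data.
- **The event would not disappear.** Protocol section 9.5.3.1 also requires SAEs to be listed.
- **Exposure is unaffected.** The exposure formula adds 28 days after the last injection, which might suggest a distorted rate. SAP section 5.7.1 uses patient counts as denominators, and the SAP specifies no exposure-adjusted SAE rate.
- **Only study withdrawals matter.** Under Protocol section 5.4.2, children who stop study drug but stay in the study are asked to attend the remaining visits.

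None of this closes the gap between ET and Day 113 in the SAP's treatment and follow-up tables.

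**Conclusion.** The point holds as a defect in stated rules, with a small expected effect. An SAE reported after ET with onset no later than Day 113 falls in neither the treatment nor the follow-up period of the SAP, although Protocol section 9.5.3.1 gives it a place. Whether the overall table counts it depends on an end date that the SAP does not supply.

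When such an event occurs, the affected table understates that arm's incidence by 1.25 percentage points, provided that 80 children are analysed and the child has no other SAE counted. Under the assumptions above, the expected number missed is well below one per arm.

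A reader might go further and conclude that the reported SAE incidence will be too low, or that half or all of an arm's count will be lost. The documents do not support that. It presumes that an event has occurred in the gap, and the share is smaller on placebo: 1/4.8 to 1/4.0, or about 21% to 25% of the expected count at the adult rates.

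**What to change.** 1. In SAP sections 3.2 and 4.5.1, start follow-up the day after the week 16 date or the ET date, as Protocol section 9.5.3.1 does.
2. Amend the follow-up subset rule, which now requires a visit after week 16. Admit early-terminated children whether or not they had an event, so that a child with a reported event counts in numerator and denominator and the set is not selected on outcome.
3. For early-terminated children, end the overall period at the later of the last visit and the end of the 30-day SAE reporting window, unless the child has entered the OLE. State how later fatal or drug-related reports are handled.
4. Because the protocol's treatment period also ends at ET, present the week 16 SAE endpoint with a cumulative cut-off, at least as a supportive count. It would include all reported SAEs with onset up to the week 16 visit or Day 113. Keep it apart from the treatment and follow-up tables, which are mutually exclusive, so that no event is assigned to both.
5. List the resulting definitions in SAP section 1.2.3 wherever they differ from the protocol.

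The cost is minor programming and reconciling SAE reports received after ET into the analysis data. Reported SAE incidence may rise slightly.

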### **5.7.1. Adverse Events**

The number and proportion of patients reporting TEAEs will be summarized overall during the study, during the week 16 treatment period, and during the follow-up period separately, sorted by decreasing frequency of SOC and PT in the dupilumab group.

AE incidence tables will be presented by treatment group for the SAF as well as for selected subgroups. TEAE summaries will present the number (n) and percentage (%) of subjects experiencing a TEAE by SOC and PT, sorted by decreasing frequency of SOC and PT for the dupilumab treatment group. Multiple occurrences of AEs of the same PT (or SOC) in the same subject will be counted only once for that PT (or SOC). For tables presenting severity of events, the worst severity will be chosen for subjects with multiple instances of the same event. The denominator for computation of percentage is the number of patients in each treatment group for the corresponding analysis period as specified in Section 3.2.

An overall summary of TEAEs will be provided with number and proportions of patients with any:

- TEAE
- Serious TEAE
- TEAE of special interest (AESI)

- TEAE leading to death
- TEAE leading to permanent treatment discontinuation

Detailed summaries of TEAEs will include:

- TEAEs
  - TEAEs by SOC/PT
  - TEAEs (for HLTs: Injection site reactions, Herpes viral infections) by SOC/HLT/PT
  - TEAEs by PT
  - Common TEAEs by SOC/PT (incidence with PT  $\geq 5\%$ )
  - TEAEs by severity by SOC/PT
  - Severe TEAEs by SOC/PT
  - TEAEs related to study medication as assessed by the investigator by SOC/PT
  - Severe TEAEs related to study medication as assessed by the investigator by SOC/PT
- Serious TEAEs by SOC/PT
  - Serious TEAEs by SOC/PT
  - Serious TEAEs by SOC/PT
  - Serious TEAEs related to study medication as assessed by the investigator by SOC/PT
- TEAEs leading to permanent discontinuation of study treatment by SOC/PT
- Fatal TEAE by SOC/PT
- AESI by AESI category ([Appendix 4](#)) and HLT/PT

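### The follow-up adverse-event tables leave out a child who entered follow-up but had no visit after Week 16, even when an event is on record

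*SAP*

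**What the plan says.** SAP 3.2 defines three safety periods: 16-week treatment, follow-up and overall study. The full safety set serves two of them: "The SAF will be the basis for the analyses for the treatment period and overall study period". For follow-up, only a subset is used, namely "the patients who entered the follow-up period and had at least one visit after the week 16 treatment visit (EOT". Entering follow-up and having a later visit are thus two separate conditions.

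SAP 4.5.1 classifies events by date, with no visit condition: "TEAEs during the follow-up period are AEs with onset after the week 16 visit date up to the end of the study".

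SAP 5.7.1 says that TEAEs are "summarized overall during the study, during the week 16 treatment period, and during the follow-up period separately". The percentage denominator is the "number of patients in each treatment group for the corresponding analysis period as specified in Section 3.2".

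Protocol 9.3.2 assigns all clinical safety variables to the SAF. Protocol 9.5.3.1 defines the follow-up period by dates ("Follow-up period: date after week 16 visit date" onward), also without a visit condition. SAP 1.2.3 lists the SAP's changes from the protocol, and the follow-up subset is not among them.

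**The concern.** Whether a child is in the follow-up set depends on something that happens after Week 16, namely coming back for a visit. The event being counted can prevent that visit. A child who enters follow-up, dies or has a serious event before the next visit and is never seen again meets the SAP 4.5.1 definition of a follow-up TEAE but is outside the SAP 3.2 set.

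The treatment-period table has no such condition, since one dose puts a child in the SAF. Follow-up is the part of the study meant to observe children while drug concentrations decline (Protocol 1.2.1). Its table should not be able to omit a known event for this reason. Only children who do not enter the open-label extension have a follow-up period, so the set may be small and a single omission visible.

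**Working it through.** The plan states no figure for the follow-up set, so there is nothing to reproduce. The check is a reading of the definitions followed by simple proportions.

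**1. Time without a scheduled visit.** In the Part B schedule of events, Week 16 is Day 113 ± 3 and the first follow-up visit is Day 141 ± 4. Telephone visits are scheduled only in the treatment period.
- On target days: 141 − 113 = 28 days.
- Shortest, using both windows: (141 − 4) − (113 + 3) = 21 days.
- Longest: (141 + 4) − (113 − 3) = 35 days.

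**2. Which events can be on record without a visit.** Protocol 7.2.2 and 7.2.3 require SAEs and AESIs to be reported to the sponsor within 24 hours, whether or not there is a visit. Protocol 7.2.6 collects AE information up to the last study visit, so a non-serious event in a child with no later visit may never be recorded. The events at risk of omission are therefore mainly SAEs, deaths and AESIs.

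**3. What each table does with such an event.** Take a child with a recorded SAE after Week 16 and no later visit.

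| Table | Set (SAP 3.2) | Child in denominator | Event in numerator |
|---|---|---|---|
| 16-week treatment | SAF | yes | no (onset after Week 16) |
| Follow-up | subset with a later visit | no | no |
| Overall study | SAF | yes | yes, if the period covers the onset date |

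The last entry carries a condition because "Overall study Period is defined as Day 1 to the date of the end of study (EOS) visit", and no substitute date is given for a child without that visit.

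**4. Size and direction.** Let m children in an arm enter follow-up. Let x of those with a later visit have an event. Among those without a later visit, let k have a recorded event and u have none.
- Rate among all who entered: (x + k)/m.
- Rate under the SAP: x/(m − k − u).

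The first rate is a weighted average of the event rates in the visit and no-visit groups. The SAP rate is therefore too low when k/(k + u) exceeds x/(m − k − u), and too high when it is smaller.

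The values of m below are assumptions.

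| m per arm | Only event is in the no-visit child: all entered → SAP | One further event in a child with a visit: all entered → SAP | No-visit child has no event, one event elsewhere: all entered → SAP |
|---|---|---|---|
| 5 | 1/5 = 20.0% → 0/4 = 0% | 2/5 = 40.0% → 1/4 = 25.0% | 1/5 = 20.0% → 1/4 = 25.0% |
| 10 | 1/10 = 10.0% → 0/9 = 0% | 2/10 = 20.0% → 1/9 = 11.1% | 1/10 = 10.0% → 1/9 = 11.1% |
| 20 | 1/20 = 5.0% → 0/19 = 0% | 2/20 = 10.0% → 1/19 = 5.3% | 1/20 = 5.0% → 1/19 = 5.3% |
| 40 | 1/40 = 2.5% → 0/39 = 0% | 2/40 = 5.0% → 1/39 = 2.6% | 1/40 = 2.5% → 1/39 = 2.6% |

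One omitted child with an event lowers the rate by 2.4 points (5.0 − 2.6) to 20 points (20.0 − 0). One omitted child without an event raises it by 0.1 to 5 points.

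**The case against.** The strongest reply is that the event is not lost. The overall-study table uses the full SAF and includes serious and fatal TEAEs, and Protocol 9.5.3.1 also lists and summarizes deaths and other SAEs. A reader might infer that the rule removes events from the study's safety record. The documents do not support that: one of three period tables is affected. This stands, subject to the missing end date shown above.

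Second, SAP 3.2 asks for any visit, not a scheduled one. Withdrawn patients are asked to attend an early termination visit (Protocol 6.1.1), and unscheduled visits may be used to follow up AEs (Protocol 6.1.2). Either one after Week 16 restores the child. It would therefore be wrong to say that a child must stay event-free to be included, or that every withdrawn child is excluded. This also stands and narrows the group to children never seen again.

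Third, requiring observed follow-up is a conventional way to avoid counting unobserved children as event-free, and dropping event-free children raises the rate. A claim that incidence is always biased downward is therefore too strong. This is a fair argument about children with no information. It does not justify dropping a child whose event is known.

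Fourth, the safety objective covers 16 weeks of treatment, the secondary safety endpoints run through Week 16 (SAP 4.4.2), and the hazard ratios cover the treatment period only (SAP 5.7.1). The follow-up tables are descriptive. Events between the last dose at Week 12 and the Week 16 visit are in the treatment period on the full SAF, so not every off-drug week is affected. This limits the stakes.

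Finally, Protocol 9.5.3.1 defines a period rather than a population, so its silence on visits is not a contradiction. The relevant departure is from Protocol 9.3.2, which applies the SAF to all clinical safety variables. The SAP narrows that for follow-up without declaring it in SAP 1.2.3.

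**Conclusion.** The point holds for the follow-up AE tables. A recorded event with onset after Week 16 is left out of numerator and denominator when the child entered follow-up and had no later visit of any kind, although the event meets the SAP's own definition of a follow-up TEAE. The follow-up rate is biased downward when the event prevents the visit, and can move the other way when the children without visits are event-free.

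The real size cannot be given. The number entering follow-up, the number of those without a later visit and the number of their recorded events are all absent from the documents. The shift of about 2 to 20 points is an illustration for one child at an assumed 5 to 40 per arm, and its upper end requires that child to have the arm's only event. The efficacy results and the 16-week safety results are not affected. The correction is worth making because the omitted events would mostly be serious or of special interest, and the change is small.

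**What to change.** In SAP 3.2, separate AE tables from by-visit summaries:

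- **AE tables.** Define the follow-up set as all SAF patients who entered the follow-up period (did not enter the OLE), with or without a later visit. Count every recorded AE with onset after the Week 16 date. SAP 5.4 already plans a count of patients entering follow-up, so the denominator can be checked against disposition.
- **Transparency.** Report by arm how many of these children had no visit after Week 16.
- **Period end.** State a fallback end date for the follow-up and overall periods when there is no EOS visit.
- **By-visit laboratory, vital sign and ECG summaries.** Keep the condition of at least one later visit.
- **SAP 1.2.3.** Declare and justify whatever restriction remains relative to Protocol 9.3.2.

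The cost is a short SAP edit and one population flag, with no new data. The downside is that a few unobserved children enter the denominator and count as event-free, which can itself lower the rate. The by-arm count of children without a later visit makes that visible.
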